6.3.1.5. Reporting of Serious Adverse Events

All SAEs have to be reported, whether or not considered causally related to the IMPs, or to the study procedure(s). All SAEs will be recorded in ClinBase™.

If any SAE occurs in the course of the study, then Investigators or other site personnel will inform appropriate AstraZeneca representatives immediately, or **no later than 24 hours** of when he or she becomes aware of it.

The designated AstraZeneca representative will work with the Investigator to ensure that all the necessary information is provided to the AstraZeneca Patient Safety data entry site **within 1 calendar day** of initial receipt for fatal and life-threatening events and **within 5 calendar days** of initial receipt for all other SAEs.

For fatal or life-threatening AEs where important or relevant information is missing, active follow-up will be undertaken immediately.

Investigators or other site personnel will inform AstraZeneca representatives of any follow-up information on a previously reported SAE immediately, or **no later than 24 hours** of when he or she becomes aware of it.

The reference document for definition of expectedness/listedness is the IB for SZC, and respective SmPCs for tacrolimus and cyclosporin.

6.3.1.6. Regulatory Reporting Requirements for SAEs

Prompt notification by the Investigator to the Sponsor of an SAE is essential so that legal obligations and ethical responsibilities towards the safety of subjects and the safety of the IMP under clinical investigation are met.

The Sponsor has a legal responsibility to notify both the local regulatory authority and other regulatory agencies about the safety of the IMP under clinical investigation. The Sponsor will comply with country-specific regulatory requirements relating to safety reporting to the regulatory authority, IRB/IEC, and Investigators.

For all studies except those utilising medical devices investigator safety reports must be prepared for suspected unexpected serious adverse reactions according to local regulatory requirements and Sponsor policy and forwarded to Investigators as necessary.

An Investigator who receives an investigator safety report describing an SAE or other specific safety information (eg, summary or listing of SAEs) from the Sponsor will review and then file it along with the IB or and will notify the IRB/IEC, if appropriate according to local requirements.

6.3.2. Clinical Laboratory Assessments

6.3.2.1. Haematology

White blood cell (WBC) count	Neutrophils absolute count
Red blood cell (RBC) count	Lymphocytes absolute count
Haemoglobin (Hb)	Monocytes absolute count
Haematocrit (HCT)	Eosinophils absolute count
Mean corpuscular volume (MCV)	Basophils absolute count
Mean corpuscular haemoglobin (MCH)	Platelets
Mean corpuscular haemoglobin concentration (MCHC)	Reticulocytes absolute count

6.3.2.2. Serum Clinical Chemistry

Sodium	Alkaline phosphatase (ALP)
Potassium	Alanine aminotransferase (ALT)
Urea	Aspartate aminotransferase (AST)
Creatinine	Gamma glutamyl transpeptidase (GGT)
Albumin	Total Bilirubin
Calcium	Unconjugated bilirubin
Phosphate	
Glucose(fasting)	
C-reactive protein (CRP)	
T ₄ ^a	Follicle stimulating hormone (FSH) ^{a, b}
TSH ^a	

^a Screening only.

^b Female subjects only.

6.3.2.3. Urinalysis

Glucose	
Protein	
Blood	

Upon a positive urine test from leucocytes, blood, nitrite or protein, the Investigator may require further urine analysis, such as flow cytometry. Results of additional urine analyses will be included in the database. If the flow cytometry examination shows a different result than the urine sticks, the urine will be investigated by fully automated digital imaging where leukocytes, erythrocytes, casts in urine will be analysed.
	

6.3.2.4. Viral Serology and SARS-CoV-2 Virology

Hepatitis B surface antigen (HBsAg)	Hepatitis B core antibody
Hepatitis C antibody	SARS-CoV-2 antibody testing
Human immunodeficiency virus (HIV) I and II testing	
SARS-CoV-2 by RT-PCR (specimen may be collected by oropharyngeal and/or nasopharyngeal swabs)	

Additional investigations may be performed as judged by the Investigator, in collaboration with the Sponsor.

6.3.2.5. Drugs of Abuse, Alcohol and Cotinine

Amphetamine / Ecstasy	Benzodiazepines
Ethanol	Methadone Metabolites
Cannabinoids	Barbiturates
Cocaine	Phencyclidine
Opiates	Urine Creatinine
Cotinine	
Tricyclic antidepressants (TCA)	

6.3.3. Physical Examination

Full

The complete physical examinations will include an assessment of the general appearance, respiratory, cardiovascular, abdomen, skin, head, and neck (including ears, eyes, nose, and throat), lymph nodes, thyroid, musculoskeletal and neurological systems.

Brief (Abbreviated)

The brief physical examinations will include an assessment of the general appearance, skin, abdomen, cardiovascular system and respiratory.

6.3.4. Resting 12-lead Electrocardiogram

At the time points specified in the SoA (Table 3), a 10-second 12-lead safety ECG, including QTcF, PR, QRS QT interval, and HR will be obtained after 10 minutes supine rest, using the site's own ECG machines.

The Investigator will judge the overall interpretation as normal or abnormal and this evaluation will be reported in ClinBase™. If abnormal, it will be further documented as to whether or not the abnormality is clinically significant by the Investigator. For all abnormalities (regardless of clinical significance) the specific type and nature of the abnormality will be documented in ClinBase™. Clinically significant findings should also be documented on the AE page of the CRF if applicable.

The Investigator may add extra 12-lead resting ECG safety assessments if there are any abnormal findings or if the Investigator considers it is required for any other safety reason. These assessments should be entered as an unscheduled assessment.

All subjects who have QTc prolongation defined as QTcF > 500 ms, or a prolongation from baseline of > 60 ms on repeat 12-lead ECG, should immediately have serum potassium assessed, if not already done within 1 hour of performing the ECG.

All ECG readings will be digitally stored as source documents.

6.3.5. Vital Signs

The following variables will be collected after the subject has rested in the supine position for at least 5 minutes:

- Systolic BP (mmHg)
- Diastolic BP (mmHg)
- Pulse (bpm)
- Tympanic temperature (°C)

The measurement of vital signs will be carried out according to the relevant Parexel SOPs.

6.4. Pharmacokinetics

6.4.1. Collection of Pharmacokinetic Samples

Whole blood samples for the determination of concentrations of tacrolimus/cyclosporin will be collected for each treatment period as specified in the SoA ([Table 3](#)).

Samples will be collected, handled, labelled, stored and shipped as detailed in the Laboratory Manual.

6.4.2. Pharmacokinetic Drug Assays

The PK samples will be analysed by Covance on behalf of AstraZeneca, using validated assays.

Full details of the analytical method and analyses performed will be described in a separate bioanalytical report.

7. BIOLOGICAL SAMPLES PROCEDURES

All biological samples will be performed by trained staff and in accordance with the Clinical Unit's SOPs.

7.1. Total Blood Volume

The approximate total amount of blood to be collected from each subject in this study, excluding repeat samples, is summarised in [Table 6](#).

Table 6 Total Blood Volume

	Volume per Sample	Number of Samples	Total
Haematology	2.7 mL	6	16.2 mL
Clinical chemistry ^a	7.5 mL	6	45 mL
Serum potassium	2.6 mL	6	15.6 mL
PK assessments for tacrolimus/cyclosporin	1 mL	45	45 mL
SARS-CoV-2 antibody testing (ELISA)	2.6 mL	1	2.6 mL
Total			124.4 mL

^a Viral serology testing and follicle stimulating hormone testing (for female subjects) will be performed using the clinical chemistry sample collected at the screening visit.

Abbreviations: ELISA = enzyme-linked immunosorbent assay; PK = pharmacokinetics; SARS-CoV-2 = severe acute respiratory syndrome coronavirus 2.

Repeat blood samples may be collected for safety reasons. The maximum volume to be drawn from each subject must not exceed 500 mL.

7.2. Handling, Storage and Destruction of Biological Samples

Samples will be disposed of, on instruction from AstraZeneca, after the CSR has been finalised, unless samples are retained for additional or future analyses.

7.2.1. Pharmacokinetic Samples

Pharmacokinetic samples will be disposed of after the bioanalytical report finalisation or 6 months after issuance of the draft bioanalytical report (whichever is earlier), unless requested for future analyses.

Pharmacokinetic samples may be disposed of or anonymised by pooling. Additional analyses may be conducted on the anonymised, pooled PK samples to further evaluate and validate the analytical method. Any results from such analyses may be reported separately from the CSR.

Incurred sample reproducibility analysis or additional assay development work, if any, will be performed alongside the bioanalysis of the test samples. The results from the evaluation, if performed, will be reported in a separate Bioanalytical Report.

7.3. Labelling and Shipment of Biohazard Samples

Samples will be labelled and shipped in accordance with the Laboratory Manual and the Biological Substance, Category B regulations (materials containing or suspected to contain infectious substances that do not meet Category A criteria), see [Appendix B](#) of this CSP 'IATA 6. 2 Guidance Document'.

Any samples identified as Infectious Category A materials will not be shipped and no further samples will be taken from the subject unless agreed with AstraZeneca and appropriate labelling, shipment and containment provisions are approved.

7.4. Chain of Custody of Biological Samples

A full chain of custody will be maintained for all samples throughout their lifecycle.

The Investigator will ensure full traceability of collected biological samples from the subjects while in storage at the centre until shipment and will keep documentation of receipt of arrival.

The sample receiver will keep full traceability of samples while in storage and during use, until used, disposed of, or until further shipment or disposal (where appropriate) and will keep documentation of receipt of arrival.

7.5. Withdrawal of Informed Consent for Donated Biological Samples

If a subject withdraws consent to the use of donated biological samples, the samples will be disposed if not already analysed and the action documented.

As collection of donated biological samples is an integral part of the study, the subject is withdrawn from further study participation.

AstraZeneca ensures the central laboratory(ies) holding the samples is/are informed about the withdrawn consent immediately and that samples are disposed of/destroyed, the action documented, and the signed document returned to the Clinical Unit.

8. ETHICAL AND REGULATORY REQUIREMENTS

8.1. Ethical Conduct of the Study

The study will be performed in accordance with ethical principles that have their origin in the Declaration of Helsinki and are consistent with ICH-GCP and the AstraZeneca policy on Bioethics and Human Biological Samples.

8.2. Subject Data Protection

The ICF will incorporate (or, in some cases, be accompanied by a separate document incorporating) wording that complies with relevant data protection and privacy legislation.

All clinical study findings and documents will be regarded as confidential. The Investigator and members of his/her research team must not disclose such information without prior written approval from the Sponsor.

The anonymity of participating subjects must be maintained. Subjects will be specified in outputs and other documents containing subject data by their subject number, not by name. Documents that identify the subject (eg, signed ICF) will be maintained in confidence by the Investigator.

Study data will be stored in accordance with local and global data protection laws.

8.3. Ethics and Regulatory Review

The study will be submitted to the national regulatory agency, BfArM, for review and approval, by Parexel in accordance with local regulatory procedures.

The study will be submitted to IEC for ethical review and approval by the Investigator in accordance with local procedures.

Parexel will provide the IEC and Investigator with safety updates/reports according to local requirements, including SUSARs, where relevant.

AstraZeneca will provide the regulatory authority with safety updates/reports according to local requirements, including SUSARs, where relevant.

Compensation will be reasonable and related to the nature and degree of inconvenience and discomfort as a result of participation in the study. Information on how subjects will be compensated is contained in the ICF.

8.4. Insurance

The Sponsor has covered this clinical study by means of an insurance of the clinical study according to national requirements. The name and address of the relevant insurance company,

the certificate of insurance, the policy number and the sum insured are provided in the Investigator's Site File.

8.5. Informed Consent

The subjects shall be informed of the nature, significance, implications and risks of this clinical study, and informed consent will be freely given and evidenced in writing, dated and signed, or otherwise marked, by the subject as evidence to indicate his/her free informed consent, prior to the start of the study.

The nature of the informed consent will comply with the Declaration of Helsinki, the current requirements of GCP (EMA/CHMP/ICH/135/1995) and local regulation which ever offers the greater subject protection.

8.6. Changes to the Protocol and Informed Consent Form

Study procedures will not be changed without the mutual agreement of the Investigator and AstraZeneca.

If there are any substantial changes to the study protocol, then these changes will be documented in a study protocol amendment and where required in a new version of the study protocol.

If a protocol amendment requires a change to the ICF, the IEC should approve the revised ICF before the revised form is used.

If local regulations require, any administrative change will be communicated to or approved by the IEC.

9. DATA QUALITY ASSURANCE AND DATA MANAGEMENT

9.1. Quality Control and Source Data Verification

Source data verification will be conducted with due regard to subject confidentiality.

The Clinical Unit will allow the study monitor and Sponsor representative direct access to all study documents, medical files and source documents to enable verification of the study data, while maintaining the anonymity of the subject and confidentiality of the data.

Internal quality control will be performed at all stages of the study by the Clinical Unit.

9.2. Audit/Inspections

The Clinical Unit facilities and all study data/documentation may be audited/inspected by independent auditor/inspector/any representatives of regulatory authorities. The Investigator must allow the applicable persons access to all relevant facilities and data/documents. The Investigator must be available to discuss any findings/issues.

If an audit was performed, the audit certificate will be included in the CSR.

9.3. Study Monitoring

The conduct of the study will be monitored by an independent Parexel monitor to ensure compliance with applicable regulatory requirements and GCP. The summary of the documentation of the monitoring visits will form part of the study documentation and will be archived as such.

Monitoring visits at site will be limited to a minimum required as deemed appropriate during COVID-19 pandemic.

9.4. Data Collection

The ClinBase™ system is an electronic source data capturing and information management system. The system combines all aspects of source data capturing with process control and clinical study management. All clinical and laboratory data, except those which are paper-based or provided by external vendor, will be collected in ClinBase™. Only paper-based data will be subject to data entry. For electronic source data, no data entry will be performed.

The responsible study monitor will check data at the monitoring visits to the Clinical Unit. The Investigator will ensure that the data collected are accurate, complete and legible. Data will be monitored within ClinBase™ by the study monitor before being exported. Any changes made during monitoring will be documented with a full audit trail within ClinBase™.

9.4.1. Case Report Forms and Source Documents

All data obtained using paper collection methods during the clinical study will be recorded in ClinBase™. All source documents from which ClinBase™ entries are derived should be placed in the subject's personal records.

The original ClinBase™ entries for each subject will be checked against source documents by the study monitor. Instances of missing or uninterpretable data will be discussed with the Investigator for resolution.

9.4.2. Access to Source Documents

During the course of the clinical study, a study monitor will make Clinical Unit visits to review protocol compliance, compare ClinBase™ entries and individual subject's personal records, assess IMP accountability and ensure that the clinical study is being conducted according to pertinent regulatory requirements. ClinBase™ entries will be verified against source documents. The review of medical records will be handled confidentially to ensure subject anonymity.

Checking of the ClinBase™ entries for completeness and clarity and verifying with source documents will be required to monitor the clinical study for compliance with GCP and other regulations. Moreover, regulatory authorities of certain countries, IRBs/IECs may wish to carry out source data inspections on-site, and the Sponsor's clinical quality assurance group may wish to carry out audits. Direct access to source data will be required for these inspections and audits; they will be carried out giving due consideration to data protection and subject confidentiality. The Investigator assures the Sponsor of the necessary support at all times.

9.5. Data Management

Parexel will utilise standardized and validated procedures and systems to collect, process and file the clinical data of this study. Any system used will be compliant with FDA 21 Code of Federal Regulations Part 11 requirements.

A DMP will be prepared to describe the processes and data flow within the clinical study. Timelines, versions for the computer systems and the coding will be defined in the DMP, and if applicable, sponsor specific requests will also be documented within. The DMP will be finalised before first dose where possible, but before database lock.

A DVS will be created to outline the validation checks to be performed during the study. The DVS must be finalised before data validation.

After the data has been monitored by the responsible study monitor all data received will be reviewed, logged and filed.

The raw data intended for further processing will be checked by standard routines or according to the DVS and queries will be generated and sent to the Investigator for review and resolution. Corrections resulting from these queries will be confirmed on the data clarification forms. This process will be repeated until no further discrepancies are found. The data will then be declared as clean. Applicable documentation will be stored in the study files.

Only trained study staff will have access to the clinical database and every change in data will have a full audit trail.

10. EVALUATION AND CALCULATION OF VARIABLES

10.1. Safety Variables

10.1.1. Adverse Events

All AEs will be coded using the latest version of the MedDRA vocabulary and will be listed for each subject.

Adverse events will be assigned to a treatment based on the start date/time of the AE in relation to dosing in that period; for tabulation purposes the AE will then be assigned to the treatment received in the respective treatment period as follows:

- Treatment Period 1: AEs with start date/time at the time of or after dosing in Treatment Period 1 until the time of dosing in Treatment Period 2.
- Treatment Period 2: AEs with start date/time at the time of or after dosing in Treatment Period 2 until the Follow-up Visit.

For assigning AEs to a specific treatment/dose, the following guidelines should be followed:

- Adverse events with start date/time at the time of or after dosing (for each specific treatment) until the next treatment/dose or until Follow-Up Visit will be assigned to the specific treatment/dose (including washout period).
- Adverse events with unknown start times, but with start date known, will be imputed with a time of 00:00, unless the start date corresponds to any given dosing date. In this case the start time will be imputed with the time of dosing. If this results in a start date/time after end date/time of the AE, then the time will also be imputed with 00:00.
- Adverse events with completely unknown start dates will be imputed with the date and time of dosing, unless the end date is known and prior to dosing; in that case the start date will be imputed as the date of Screening and a time of 00:00.
- Adverse events with partially known start dates/times will be treated as follows:
 - If only the day is missing, then the day will be imputed with the first day of the month, unless the month and year in which the AE started is a month and year in which IMP was administered, then the day will be imputed with the first day on which IMP was administered in that month. If this results in a start date after the end date, then the day will be imputed with the first day of the month.
 - If only the month is missing and the year is a year in which IMP was administered, then the month will be imputed with the first month in which IMP was administered. If this results in a start date after the end date of the AE, then the month will be imputed with JAN. If the known year part is not a year in which IMP was administered, then the month will also be imputed with JAN.
 - If both the day and month is missing and the year is a year in which IMP was administered, then the day and month will be imputed with the day and month of

dosing. If this results in a start date after end date, then the day and month will be imputed with 01JAN. If the year is not a year in which IMP was administered, then the day and month will also be imputed with 01JAN.

- If only the year is missing, then the year will be imputed with the year of dosing.

Adverse events with onset (start date/time) after dosing in Treatment Period 1 will be summarised by treatment and overall for all subjects, including tabulations by causality and severity (mild, moderate and severe). All tabulations will be presented by SOC and PT. Furthermore, separate listings of SAEs, AEs that led to discontinuation and AEs that led to death will be presented.

The following information will be included in the listings: verbatim term, SOC, PT and lowest level term, start date/time, end date/time, time from last dose, causality, action taken, whether the AE was classified as serious and the outcome.

All tabulations will include the number and percentage of subjects. In addition, a separate tabulation will be presented showing the number of events by treatment and PT.

Finally, an overview of all AEs will be presented, separately for the number and percentage of subjects. This will include categories for any AE, AEs leading to discontinuation, AEs with outcome of death and SAEs.

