Sodium zirconium cyclosilicate (SZC), is an oral, non-polymer inorganic cation-exchanger that has been approved as a novel therapy for the treatment of hyperkalaemia. It selectively captures potassium ions in exchange for sodium and hydrogen ions in the gastrointestinal lumen, thereby reducing serum potassium concentration and removing potassium from the body through increased faecal excretion. Sodium zirconium cyclosilicate exerts its effect locally and is not absorbed systemically. Due to its insoluble, inorganic, and crystalline properties, SZC is not absorbed or metabolised by the body and therefore no metabolic or transporter-based drug-drug interactions (DDIs) are anticipated in association with SZC treatment. However, SZC can bind to hydrogen ions which may result in increased pH in acidic environments such as the stomach. In general, an increase in gastric pH can alter the solubility of drugs with pH-dependent solubility and may result in an altered absorption profile of the drugs. Results from a Phase 1 study performed in healthy subjects to examine the potential for DDIs between SZC and a set of 9 compounds showed that co-administration of SZC affected the pharmacokinetics (PK), primarily the C_{max} values, of 5 compounds tested (Study ZS-009).

This study will investigate if the PK of tacrolimus and cyclosporin may be altered by the increased gastric pH resulting from SZC co-administration.

Number of Subjects Planned

A total of 60 subjects will be randomised (30 per cohort) to ensure at least 56 evaluable subjects (28 subjects per cohort) at the end of the last treatment period.

Study Period

Estimated date of first subject enrolled: December 2020 (signing of informed consent).

Estimated date of last subject completed: March 2021.

Study Objectives

Primary Objective:

- To assess the effect of co-administered SZC on the PK of tacrolimus and cyclosporin in healthy subjects as described by C_{max} and AUC_{inf}.

Secondary Objectives:

- To assess the effect of co-administered SZC on the PK of tacrolimus and cyclosporin in healthy subjects, as described by AUC_{last}, t_{1/2λ_z}, and t_{max}.
- To examine the safety and tolerability of co-administration of SZC and tacrolimus/cyclosporin as compared to tacrolimus/cyclosporin alone in healthy volunteers.

Study Design

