3. STUDY DESIGN

3.1. Overall Study Design and Flow Chart

This study will be an open-label, randomised sequence, 2-period, 2-cohort, 2-treatment in each cohort, cross-over study in healthy subjects (males and females of non-childbearing potential), performed at a single study centre.

The study will comprise:

- A screening period of maximum 28 days;
- Two treatment periods:
 - Treatment Period 1 starts with admission to the Clinical Unit on Day -1, followed by dosing on Day 1 with the assigned treatment (A, B, C, or D) as per assigned cohort and treatment sequence, followed by a washout period of at least 14 days. Subjects will be discharged from the Clinical Unit after the last PK sample was collected for this treatment period (Day 4).
 - Treatment Period 2 starts with admission to Clinical Unit on Day -1, followed by dosing on Day 1 with cross-over treatment as per assigned cohort, followed by a follow-up period of 7 to 10 days. Subjects will be discharged from the Clinical Unit after the last PK sample was collected for this treatment period (Day 4).
- A follow-up visit/early termination visit at 7 to 10 days after the last IMP administration.

Subjects will be assigned to either Cohort 1 (tacrolimus) or to Cohort 2 (cyclosporin). Each cohort will have 2 treatment periods. Subjects in each cohort will be randomly assigned to one of 2 treatment sequences (AB|BA or CD|DC) where,

- Treatment A: Tacrolimus [CCI].
- Treatment B: Tacrolimus [CCI] + SZC [CCI].
- Treatment C: Cyclosporin [CCI].
- Treatment D: Cyclosporin [CCI] + SZC [CCI].

Subjects who have received Treatment A in Treatment Period 1 of Cohort 1 will receive Treatment B in Treatment Period 2 and vice versa. Subjects who have received Treatment C in Treatment Period 1 of Cohort 2 will receive Treatment D in Treatment Period 2 and vice versa.

Each subject will receive a single dose of oral capsules of tacrolimus [CCI]/cyclosporin [CCI] on 2 occasions, once alone and once in combination with oral suspension of SZC [CCI]. All drug administrations will occur after a 12 hour overnight fast.

Details on IMPs administration is provided in Section 5.4.3.

The Study Flow-Chart is presented in [Figure 3-1](#) and the Overall Graphical Representation of the study scheme is illustrated in [Figure 3-2](#).

The Schedule of Assessments displaying assessments/tasks and time points is presented in [Table 3](#).

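### The partial-date rules for adverse events in Protocol 10.1.1 do not work for a two-dose cross-over: they can put an event under the wrong treatment or outside the post-dose tables

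*Protocol*

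**What the plan says.** Section 3.1 gives each subject tacrolimus or cyclosporin "on 2 occasions, once alone and once in combination with oral suspension of SZC". Table 4 (3.1.3) sets a washout of at least 14 days, counted from the day after the first dose. Section 10.1.1 allocates every AE to Period 1 or Period 2 by its start date and time, so an imputed start decides the treatment column.

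For incomplete starts, 10.1.1 lays down these rules:

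- **Day missing, dosing month:** "then the day will be imputed with the first day on which IMP was administered in that month". If that falls after the AE's end date, the first of the month is used. In a month without dosing, the first of the month is used directly.
- **Month missing, dosing year:** "then the month will be imputed with the first month in which IMP was administered", with January as fallback if the result is later than the end date.
- **Day and month missing, dosing year:** the day and month of dosing, with 1 January as fallback. The dose is not named.
- **Year missing:** "If only the year is missing, then the year will be imputed with the year of dosing". There is no end-date check.
- **Nothing known:** "Adverse events with completely unknown start dates will be imputed with the date and time of dosing", unless the AE is known to have ended before dosing, in which case the date of Screening is used. The dose is not named.

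The treatment tables in 10.1.1 include only AEs that began after the Period 1 dose. Section 6.3.1.4 collects non-serious AEs only from that dose onwards, and serious ones from consent. Section 11.2.2 simply points back to 10.1.1 for missing AE dates. Section 11.2.1 plans no separate SAP, although it allows an abbreviated one.

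**The concern.** Comparing the safety of co-administration with that of the drug alone is a secondary objective (Table 2), and the AE tables by treatment are where that comparison is read. In a cross-over, an AE moved between periods moves to the other treatment in the same subject.

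Defaulting to the first dose is not conservative either. In sequences AB and CD it shifts events from the SZC combination to the drug alone. In BA and DC it shifts them the other way. An AE imputed to before the first dose is lost from the post-dose tables altogether, although a non-serious AE cannot have been collected from before that dose.

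**Working it through.** The plan states no figure on this point. The check applies the rules as written, first to single records and then to the study calendar.

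**Single records.** All dose pairs are 15 days apart, which satisfies the washout on either way of counting it.

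| Doses | True start | Recorded as | Imputed to | Result |
|---|---|---|---|---|
| 5 and 20 Jan 2021 | 21 Jan | ?? JAN 2021 | 5 Jan | Period 2 AE counted in Period 1 |
| 20 Jan and 4 Feb 2021 | 2 Feb, ongoing | ?? FEB 2021 | 4 Feb | washout AE counted in Period 2 |
| 20 Jan and 4 Feb 2021 | 5 Feb | 05 ??? 2021 | 5 Jan | before dose 1; leaves the tables |
| 20 Dec 2020 and 4 Jan 2021 | Jan 2021, ongoing | 2021 only | 20 Dec 2021 if 'dosing' is dose 1 | after the planned end of study |
| 20 Dec 2020 and 4 Jan 2021 | 5 Jan 2021 | 05 JAN ???? | 5 Jan 2020 if 'year of dosing' is 2020 | before consent |

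In the third row the January fallback cannot help, because the imputed date is already earlier than any end date. Screening runs from Day -28 to Day -2, here 23 December to 18 January. The imputed 5 January therefore precedes consent if the subject consented between 6 and 18 January. In every case it precedes dose 1.

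That row is not an isolated accident. With a 15-day gap and follow-up 7 to 10 days after dose 2, a subject is observed for 15 + 7 = 22 to 15 + 10 = 25 days after dose 1. Moving a February date to January subtracts 31 days, and moving a March date to February subtracts 28. Both exceed 25, so every such AE lands before dose 1.

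**Calendar enumeration.** The Synopsis gives "Estimated date of first subject enrolled: December 2020 (signing of informed consent") and "Estimated date of last subject completed: March 2021". The assumptions for the base case are a 15-day gap, follow-up at 7 days and consent 2 days before dose 1. Dose 1 can then fall from 3 December to 9 March: 29 + 31 + 28 + 9 = 97 dates. Each has 15 onset days in Period 1 and 8 in Period 2, so 97 × 23 = 2,231 onset days.

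- Both doses fall in the same month for 14 + 16 + 13 + 9 = 52 dates (54%). They straddle the year-end for dose 1 on 17 to 31 December: 15 dates (15%).
- Day missing, AE ongoing: 332 / 2,231 = 15% move from Period 2 to Period 1, and 315 / 2,231 = 14% from Period 1 to Period 2. Together 647 / 2,231 = 29%.
- Month missing: 506 / 2,231 = 23% fall before dose 1.
- Nothing known: if 'dosing' is dose 1, all 97 × 8 = 776 Period 2 onset days (35%) go to Period 1. If it is dose 2, all 97 × 15 = 1,455 Period 1 onset days of ongoing AEs (65%) go to Period 2.
- Day and month missing, AE ongoing: 225 / 2,231 = 10% get a date after follow-up if 'dosing' is dose 1. If it is dose 2, 120 / 2,231 = 5% get a date before consent.
- Year missing: 253 / 2,231 = 11% fall before consent if the year is that of dose 1, and 120 / 2,231 = 5% after follow-up if it is that of dose 2.

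**Sensitivity.** Two other settings were run: a 14-day gap with follow-up at 10 days, and a 21-day gap with follow-up at 10 days and consent 14 days before dose 1. Across all three settings, the day-missing shares for ongoing AEs range over 3–18% (Period 2 to 1) and 11–26% (Period 1 to 2). The month-missing share before dose 1 is 600 / 2,375 = 25% in the 14-day setting and (233 + 613) / 2,432 = 35% in the 21-day setting.

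**The case against.** Five arguments can be made for leaving the rules alone.

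1. *Incomplete dates will be rare.* Subjects are resident to 72 hours after each dose, capture is electronic, and queries are repeated until resolved (9.5). A record with a known day but no month, or no year, would be unusual. This stands, and it limits the consequence.
2. *The rules allow for several doses.* A reader might infer that all of 10.1.1 was written for a single dosing date. The text does not support that: the day and month rules pick a first dose among several, and the missing-time rule refers to any dosing date. Only the year, day-and-month and wholly-unknown rules leave the dose open. The day and month rules fail because of the choice they make.
3. *Not every Period 2 AE with a missing day is misplaced, even when both doses share a month.* This also stands. An onset in the following month is imputed to the first of that month and is allocated correctly. In the base case 52 × 8 = 416 Period 2 onset days belong to such subjects. Of these 332 go wrong and 416 - 332 = 84 do not.
4. *The year-end failures depend on estimated dates and on the reading chosen.* December 2020 is the planned month of first consent, so December dosing is possible but not assured. If the first dosing month is read as the first within the recorded year, the month rule gives no future date. The 20 December 2021 result needs the dose 1 reading. These points stand, but the January and February examples need neither a year-end nor an unfavourable reading.
5. *Section 11.2.1 permits later changes.* It does, but it makes none. In an open-label study a repair made after the data are seen is weaker than one made now.

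**Conclusion.** The point holds as a low-consequence defect in a stated rule. It is not a complaint about detail left to a later document. Applied as written, the day-missing rule can move an AE in either direction between treatments, and the month-missing rule can place a post-dose AE before the first dose. Three other rules cannot be programmed without deciding which dose is meant.

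The effect is confined to descriptive AE tables by treatment and to the few AEs with incomplete start dates. No formal test and no PK endpoint is involved.

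The percentages count calendar possibilities under an assumed dose gap, consent timing and follow-up day, with every feasible date weighted equally. A reader might take them as the proportion of AEs that will be misclassified. They are not, because the protocol gives no rate of incomplete dates.

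**What to change.** In 10.1.1, replace the separate references to the first dosing day, first dosing month and unspecified dosing with one bounded rule:

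- Allow only start dates that agree with the recorded date parts, are not before the Period 1 dose (not before consent for SAEs), and are not after the AE's end date or the Follow-up Visit.
- If only one period remains possible, assign the AE to that period.
- If both remain possible, apply one pre-specified rule that names the dose, for example the latest dose before the visit at which the AE was first recorded. Flag these AEs in the listing.

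The time of the previous AE questioning should not serve as a hard lower limit. Section 6.3.1.4 also accepts spontaneous reports and observed events, so a late-recalled AE could be left with no permitted date. That section lists no report date for non-serious AEs, so it should be confirmed that the visit of first recording can be recovered before the example tie rule is adopted.

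The cost is a paragraph of protocol or abbreviated-SAP wording and a little programming. The tie rule may still misassign an occasional late-recalled AE, but the flag makes that visible.
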